## 5) Inclusion and Exclusion Criteria

The study population would be infants and children with adjusted gestational age of 40 weeks or greater to 8 years of age, scheduled for surgery at UNM. Patients to be excluded would be premature infants with adjusted gestational age of less than 40 weeks, those undergoing mask ventilation, and patients with ASA class 4-6. Enrollment would occur for up to six months after HRRC approval and study commencement.

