## 6) Number of Subjects (Recruitment Target)

A sample size estimate based on prior studies of apneic oxygenation in adults indicates that approximately 400 subjects would be appropriate for this study, 200 in the baseline group without nasal cannula adjunct and 200 patients with implementation of nasal cannula adjunct during the peri-intubation period.

A power analysis (based on formulae in *Statistics in Medicine* 1982; 1:121-9) indicated that if the baseline rate of reaching 95% SPO2 is 15% of patients and this procedure reduces that rate by half, 80% power at  $\alpha=0.05$  is reached for a one-tailed logrank test with a total of 371 patients. Rounding up to 400 patients to accommodate incomplete datasheets would provide power of 94%.

Based on enrollment rate to date, we estimate that enrollment of 400 patients will take approximately one year. Because the planned evaluation of routine use of nasal cannula adjunct oxygenation is occurring independent of enrollment counts to the baseline study condition, data

may be gathered on more than 200 patients in that group. In order to permit analysis without loss of power, we may need to enroll a higher total sample size in order to achieve an equal sample size in the group with the cannula. To accommodate this reality, we may enroll a maximum of 500 patients in the entire study.

This period will also permit education of all relevant providers and staff on the use of peri-intubation nasal cannula oxygenation.

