## 8) Study Timelines

- Duration of individual patient participation: Patients will participate from the time when they are brought into the OR preoperative suite and it is determined they will have an endotracheal tube (ET) or laryngeal mask airway (LMA) placed. The study observation period will end once the airway has been secured.
- The duration anticipated to enroll all study subjects will be sufficient time to enroll the target sample of patients.
- An interim analysis will be conducted halfway through enrollment of the with-cannula group.
- The estimated primary analysis will be done by December 2016.

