## 11) Study Methods

This is a prospective observational study. Prospectively-recorded data are necessary because data on the outcomes of interest are not available in the medical record.

Participants will be enrolled in the study once they have entered the pre-operative area and they are determined by the attending anesthesiologist to

that they are an eligible study participant. Participants enrolled in the first three months of the study will be assigned to the baseline condition as described below. Participants enrolled in the second phase of the study will be assigned to the with-cannula condition described below.

A patient sticker will be added to the data collection form. Basic demographic information and vitals will be recorded before premedication is administered as is standard at entry to the pre-operative area. Timing devices of the same make and model will be used consistently between all study cases.

For the **baseline group** of this observational study, all intubation procedures will be performed as per usual practice. Patients will receive premedication as determined by anesthesiologist/resident/midlevel, and the type and dose will be recorded.

Once patients are brought to the operating room suite and vital signs are being monitored, patients will be preoxygenated via mask per standard of care, with an expired oxygenation concentration minimum of 0.75. Vitals will be recorded at the moment prior to removal of the face mask at the end of the preoxygenation period. Anesthetic induction will then be performed with agents and dosages as per the provider's clinical judgment.

Airway management consisting of oral endotracheal intubation or laryngeal mask airway insertion will take place. As per usual practice, an attending physician who is expert in pediatric airway management will supervise the procedure and intervene before the patient experiences excessive oxygen desaturation. The lowest oxygen saturation and the time to either successful intubation or intervention by an attending physician will be recorded.

For the **with-cannula group**, all of the above steps will be maintained. The sole difference will be nasal cannula placement after induction. It will be set to deliver 5L of oxygen per minute.

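### The six-month enrolment cap (section 5) and the three-month baseline rule (section 11) do not fit section 6's 200 per group over about a year; at the implied rate three months gives about 100 baseline patients

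*Combined protocol and SAP*

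**What the plan says.** All references are to the combined protocol and SAP.

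- **Section 5 (Inclusion and Exclusion Criteria):** "Enrollment would occur for up to six months after HRRC approval and study commencement".
- **Section 11 (Study Methods):** "Participants enrolled in the first three months of the study will be assigned to the baseline condition as described below". Those enrolled in the second phase form the with-cannula group. No length is given for that phase.
- **Section 6 (Number of Subjects):** the target is "200 in the baseline group without nasal cannula adjunct and 200 patients with implementation of nasal cannula adjunct". From accrual so far, "we estimate that enrollment of 400 patients will take approximately one year". The evaluation of routine cannula use "is occurring independent of enrollment counts to the baseline study condition", so baseline data "may be gathered on more than 200 patients in that group". To allow the with-cannula group to match, "we may enroll a maximum of 500 patients in the entire study".
- **Section 8 (Study Timelines):** "The duration anticipated to enroll all study subjects will be sufficient time to enroll the target sample of patients". It expects the primary analysis by December 2016 and places one interim analysis at the midpoint of with-cannula recruitment.
- **Section 9 (Study Endpoints):** describes the timing of the stop for significance by reference to half of the estimated number of patients.
- **Section 26 (Privacy):** says that the move to routine cannula use will happen whether or not the study takes place.

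**The concern.** This is a before/after comparison without randomisation. Section 6 describes the groups by the care they receive, but section 11 is the only place that states how a patient is put in one group or the other, and it does so by calendar time. If that rule yields about half of the planned baseline group, the 1:1 comparison behind the sample size is not the one that will be made. A reader who follows section 5 would also stop enrolment at about half of the total that section 6 plans. The interim analysis is tied to the size of the with-cannula group, so it depends on the same unresolved numbers.

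**Working it through.** **Inputs from the plan.** Target 200 + 200 = 400; about one year to enrol 400; baseline window three months; cap six months; maximum 500 (sections 5, 6, 11). Event rates 15% and half of that, 7.5%; one-tailed log-rank test at 0.05 (section 6).

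**The plan's own figures.** The one-year estimate cannot be rebuilt, because the enrolment rate behind it is not given. It is taken as correct and the average rate is derived from it. Section 6's 371 patients for 80% power, and 94% at 400, do not reproduce: one-tailed variants need 409 to 498 patients. That is a separate issue. The power figures below are recomputed and should not be compared with the stated 94%.

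**Step 1: accrual.** Constant accrual is assumed. The 10-to-14-month range is an assumption about what approximately one year may cover.

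| | 12 months | 10 months | 14 months |
|---|---|---|---|
| Rate per month (400/months) | 33.3 | 40.0 | 28.6 |
| Baseline after 3 months | 100 | 120 | 86 |
| Total after 6 months | 200 | 240 | 171 |
| Months to reach 200 | 6 | 5 | 7 |

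A baseline of 200 in three months needs 200/3 = 66.7 a month, twice the implied rate. To have that and still take a year over 400, accrual would have to drop to 200/9 = 22.2 a month. Nothing in the plan suggests this. A baseline above 200 would take more than six months at the implied rate, so it would use up section 5's whole allowance before any with-cannula patient was enrolled.

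**Step 2: power.** Under proportional hazards, HR = ln(0.925)/ln(0.85) = 0.480. Expected events are d = 0.15 × n0 + 0.075 × n1, with n0 baseline, n1 with-cannula and φ = n1/n0. Freedman's formula gives

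power = Φ( √(dφ) × (1 − HR)/(1 + φHR) − 1.645 ).

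- 200:200: d = 45.0, φ = 1. √45 × 0.520/1.480 = 2.36; 2.36 − 1.645 = 0.71; power 76%.
- 100:300: d = 37.5, φ = 3. √112.5 × 0.520/2.439 = 2.26; 2.26 − 1.645 = 0.62; power 73%.
- 100:100: d = 22.5, φ = 1. √22.5 × 0.520/1.480 = 1.67; 1.67 − 1.645 = 0.02; power 51%.

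The one-tailed log-rank test was also simulated (20,000 runs per case). Event times were exponential, with either a common end of observation or exponential censoring. These are assumptions, because the plan gives no distribution of times.

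| Groups | Freedman | Simulated (two censoring patterns) |
|---|---|---|
| 200:200 | 76.2% | 77.6%, 81.2% |
| 100:300 (three-month rule, enrolment to 400) | 73.2% | 70.0%, 73.8% |
| 86:314 | 70.4% | 66.9%, 70.5% |
| 120:280 | 75.7% | 73.4%, 76.8% |
| 100:100 (both calendar limits) | 50.9% | 52.4%, 55.5% |

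The loss at 100:300 is 76.2 − 73.2 = 3 points by Freedman, and 7.6 and 7.4 points by simulation. Across 86:314 to 120:280 it runs from half a point (Freedman, 120:280) to about 11 points (simulation, 86:314). Schoenfeld's formula gives 79% at 200:200 and 62% at 100:300, a loss of 17 points. The simulation does not support a loss that large, so it is not used.

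**The case against.** The strongest reply is that the intended plan is clear enough. Section 6 relies on the enrolment rate so far, so it was written after recruitment began. Section 8 lets enrolment run until the target is met and places the primary analysis about 20 months after the April 2015 approval recorded in section 2. Section 2 also records monitoring on 10/21/2015, more than six months after that approval. On this reading the six-month and three-month statements, which fit each other as 3 + 3 months, are leftovers, and the switch of groups follows the practice change. Section 6 even anticipates too many baseline patients, not too few.

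Most of this stands for the cap. It does not settle the baseline rule: section 11 is still in force as written, no section overrides it, and the date of the practice change is not given, so it may or may not fall at month three.

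It is also fair to say that the count of 100 is derived. The actual monthly rate is not in the documents, and section 2 records research assistants being added about a month after approval, so accrual may not have been constant. The conflict between six months and about a year needs no such assumption.

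Two stronger readings are tempting, and the documents do not support either.

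- A reader might infer that the study will lose about 25 points of power. That requires the cap and the three-month rule to be enforced together, and sections 6 and 8 indicate that the cap is not intended to hold.
- A reader might infer from section 9 that the interim analysis could fall at patient 200, with a full baseline group and no with-cannula patient. Section 8 places the only planned interim analysis halfway through the with-cannula group, and section 9's own ineffectiveness rule tests that group against baseline. Under the three-month rule at the implied rate, patient 200 is in any case 100 + 100. The difference in wording is worth tidying, but no more than that.

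**Conclusion.** The point holds as an internal inconsistency that should be corrected. Section 5's six months contradicts section 6's one year outright. Section 11's three months gives about 100 baseline patients (86 to 120), about half of the planned 200, and does not fit section 6's expectation that baseline may exceed 200.

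The likely consequence is modest. If the three-month rule is followed and enrolment continues to 400, one-tailed power is about 70% to 74% instead of about 76% to 81%. Only enforcement of the cap as well would bring it to about 51% to 56%.

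These figures rest on constant accrual at the rate implied by section 6, the plan's 15% and 7.5% event rates, proportional hazards and, for the simulation, assumed time and censoring distributions. Confidence is high on the contradiction and lower on the exact baseline count.

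**What to change.** 1. **Section 5:** delete the six-month limit on enrolment.
2. **Section 11:** replace the three-month rule with one tied to the recorded start date of the routine practice change. Eligible patients before that date are baseline; eligible patients from that date are with-cannula. This agrees with sections 6 and 26.
3. **Section 6:** keep the target of 200 per group and the maximum of 500.
4. **Section 9:** use section 8's interim trigger, the midpoint of with-cannula recruitment, so that both sections name the same point.
5. **If baseline ends below 200:** restate the power for the group sizes actually obtained. As a guide, on the same assumptions, 100:200 gives 66% by Freedman and 66% to 68% by simulation; 150:250 gives 77% and 76% to 80%.

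The cost is wording only, with no patients beyond the 400 to 500 already allowed. The downside is that the restated power may be slightly less favourable than at 200 per group.

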## 6) Number of Subjects (Recruitment Target)

A sample size estimate based on prior studies of apneic oxygenation in adults indicates that approximately 400 subjects would be appropriate for this study, 200 in the baseline group without nasal cannula adjunct and 200 patients with implementation of nasal cannula adjunct during the peri-intubation period.

A power analysis (based on formulae in *Statistics in Medicine* 1982; 1:121-9) indicated that if the baseline rate of reaching 95% SPO2 is 15% of patients and this procedure reduces that rate by half, 80% power at  $\alpha=0.05$  is reached for a one-tailed logrank test with a total of 371 patients. Rounding up to 400 patients to accommodate incomplete datasheets would provide power of 94%.

Based on enrollment rate to date, we estimate that enrollment of 400 patients will take approximately one year. Because the planned evaluation of routine use of nasal cannula adjunct oxygenation is occurring independent of enrollment counts to the baseline study condition, data

may be gathered on more than 200 patients in that group. In order to permit analysis without loss of power, we may need to enroll a higher total sample size in order to achieve an equal sample size in the group with the cannula. To accommodate this reality, we may enroll a maximum of 500 patients in the entire study.

This period will also permit education of all relevant providers and staff on the use of peri-intubation nasal cannula oxygenation.

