adult literature indicates that peri-intubation nasal cannula oxygenation can decrease the occurrence of hemoglobin desaturation during prolonged intubations. There is some pediatric literature supporting the physiologic safety of apneic oxygenation for a brief period of time after endotracheal intubation. Our adaptation of using a nasal cannula in the peri-intubation period would be new to the pediatric literature and would hopefully further elucidate the potential effects during the peri-intubation period and investigate whether this benefit also extends to pediatric patients. There are anatomical differences in the pediatric airway compared to adults which may make the use of nasal cannula apneic oxygenation less beneficial in the pediatric population.

This minimal risk study would add to the literature extending this concept to the pediatric patient population. If the same results were to be found as in the adult patient population there is the potential for an improved less stressful pediatric intubation learning environment and improved patient care with fewer and less severe desaturations during the peri-intubation period.

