**18) Potential Benefits to Subjects**

Subjects in the with-cannula group may have a small potential benefit during the study as they may experience improved oxygenation during the ET or LMA placement period, but it is not known whether the planned intervention is effective at all. This hypothetical benefit is low for the individual patient, as it springs from any improvement in oxygenation that may result. This benefit is expected to be low for several reasons: 1) even in the no-cannula group (current practice), an attending physician who is expert in pediatric airway management is always ready to intervene before the patient's oxygen saturation reaches dangerous levels: therefore any temporary reduction in blood O2 saturation that may be avoided in the with-cannula group is mild; 2) the rates of mild SpO2 reduction during intubation are already very low, and 3) rates of complications from any brief mild SpO2 reduction are extremely low.

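### Section 6 rests its power on an unsourced 15% control rate for supervised children; power depends strongly on that rate, is about 72–77% rather than 94% even at 15%, and is never checked against the baseline group

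*Combined protocol and SAP*

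**What the plan says.** Section 6 opens with "A sample size estimate based on prior studies of apneic oxygenation in adults indicates that approximately 400 subjects", split as "200 in the baseline group without nasal cannula adjunct and 200 patients with implementation of nasal cannula adjunct". A separate paragraph gives a conditional power calculation for a one-tailed logrank test. It supposes that the baseline rate of reaching SpO2 95% "is 15% of patients and this procedure reduces that rate by half, 80% power at" alpha 0.05 with 371 patients in total. It then says that 400 patients, rounded up to allow for incomplete datasheets, would give 94% power. Neither the 15% nor the halving is sourced.

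The controls are children from 40 weeks adjusted gestational age to 8 years, with ASA 4–6 excluded (section 5), having ET or LMA placement with an attending ready to take over (section 11). Takeover before 95% is reached is censored (section 14).

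Three other statements bear on the inputs:
- Section 18 says that rates of mild SpO2 "reduction during intubation are already very low".
- Section 4 mentions anatomical differences "which may make the use of nasal cannula apneic oxygenation less beneficial in the pediatric population".
- Section 4 also says that children's higher metabolic rate puts them at greater risk of desaturation, and that learners routinely intubate at this institution.

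On sequence, section 11 says "Participants enrolled in the first three months of the study will be assigned to the baseline condition as described below", and section 6 says "Based on enrollment rate to date, we estimate that enrollment of 400 patients will take approximately one year". The maximum of 500 exists to let the with-cannula group match a baseline group that overruns 200. The interim analysis (sections 8 and 9) deals only with efficacy and ineffectiveness. Nothing compares the 15% with baseline data or revisits the sample size.

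**The concern.** Logrank power depends on the number of events, and at a fixed sample size that number scales with the control rate. An unsourced control rate, in tension with another section of the same protocol, therefore leaves the power of the primary comparison largely unknown. If the rate is well below 15%, the study has little chance of detecting even the assumed halving, and a non-significant result would carry little information.

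The plan is well placed to find out. The groups are consecutive, so the control rate is observed before the with-cannula group is complete. Section 6 already uses accrual to date to forecast duration, but it makes no use of events to date.

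**Working it through.** **Inputs.** From section 6: 200 per group, one-tailed alpha 0.05 (z = 1.645), control rate p1 = 15%, p2 = p1/2, 80% power (z = 0.842). Control rates other than 15% are assumptions, because the documents give none.

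**Step 1: the plan's own figures.** Section 6 cites a 1982 *Statistics in Medicine* paper without stating the formula. Freedman's logrank formula with hazard ratio (HR) 0.5 was tried:
- Events = (1.645 + 0.842)² × [(1 + 0.5)/(1 − 0.5)]² = 55.64.
- 55.64 / 0.15 = 370.95, which rounds up to 371. This reproduces the plan's total, but it applies the control rate to both groups.
- With the average rate (0.15 + 0.075)/2 = 0.1125, 55.64 / 0.1125 = 494.6, so 495 patients are needed.
- With HR derived from the rates, ln(0.925)/ln(0.85) = 0.480, the events needed are 50.0 and the total is 50.0 / 0.1125 = 445.

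No variant tried gives 94% at 400. In the calculation that yields 371, 400 patients give 400 × 0.15 = 60 events and z = √60/3 − 1.645 = 0.937, which is 82.6% power. The 94% looks like that z value reported as a power, but this is an inference.

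**Step 2: power at 400 with a 15% control rate.** Expected events are 200 × (0.15 + 0.075) = 45.
- Freedman, HR 0.5: z = √45/3 − 1.645 = 0.591, power 72%.
- Freedman, HR 0.480: z = √45 × 0.520/1.480 − 1.645 = 0.714, power 76%.
- Two proportions: z = [0.075 − 1.645 × √(2 × 0.1125 × 0.8875/200)] / √[(0.15 × 0.85 + 0.075 × 0.925)/200] = 0.734, power 77%.

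Schoenfeld's formula with HR 0.480 gives 79%. If only 371 patients have usable data, the first three methods give 69%, 73% and 74%.

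**Step 3: sensitivity to the control rate.** Same formulas, 200 per group, rate halved. The last column is the smallest relative reduction detectable with 80% power, by two proportions.

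| Control rate | Events | Freedman, HR 0.5 | Freedman, HR from rates | Two proportions | Detectable reduction |
|---|---|---|---|---|---|
| 5% | 15 | 36% | 37% | 37% | 83% |
| 10% | 30 | 57% | 60% | 60% | 63% |
| 15% | 45 | 72% | 76% | 77% | 52% |
| 20% | 60 | 83% | 87% | 88% | 45% |

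Power of 94% at 400 would need a control rate of about 25% to 31% (Freedman, HR from rates and HR 0.5).

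**Step 4: what the cap of 500 can do.** As 250 + 250, Freedman gives 80–84% at 15%, 65–68% at 10% and 42–43% at 5%. As 200 + 300, two proportions gives 84%, 68% and 44%.

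**Step 5: cost of using baseline data to set the second group.** In a null simulation (2 million runs), the with-cannula group was set to 300 if the observed baseline rate was below 15%, and to 200 otherwise. One-sided type I error was 0.049–0.054, against 0.049–0.052 with fixed groups of 200. The baseline estimate is imprecise: 20 events in 200 give a Wilson 95% interval of 6.6% to 14.9%.

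**The case against.** A reader might infer that 15% is wrong for these children. The documents do not establish that. No observed pediatric rate is reported. The statement in section 18 has no number or threshold, speaks only of intubation, and is part of an argument that individual benefit is small. It is in tension with 15% but does not refute it.

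A reader might also infer that the 15% was taken from adults. Section 6 ties only the total of about 400 to adult studies, and the 15% appears in a separate conditional statement without attribution.

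Nor does the doubt about the control rate run only downward. Section 4's remarks on metabolic rate and learner intubators point upward. Attending supervision is aimed at excessive desaturation, and no passage says that 95% counts as such. At 20% the power would be 83–88%.

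Finally, nothing says that a null result will be reported as absence of benefit. Section 9 defines ineffectiveness only for the interim decision.

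These objections stand, and they limit the point to an unsupported and untested input. They do not remove it. A condition that the study itself can observe, but never checks, cannot describe the study's power, and uncertainty in both directions is a reason to look.

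A further objection is that recalculation cannot rescue a low rate: 500 patients give only 65–69% at 10% across the methods and allocations above. That is true. Where the rate is low, the gain is honest disclosure rather than restored power.

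**Conclusion.** The point holds as a gap in justification and checking, together with a power figure that the stated design does not deliver. At the plan's own 15%, power with 400 patients is about 72–77% (79% under the most favourable formula tried), some 15 to 22 points below the stated 94%. Across assumed control rates of 5% to 20%, it runs from about 36% to 88%.

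These figures assume 200 evaluable patients per group, a true halving and one-tailed 0.05, and they make no allowance for the interim analysis. They do not show that the true rate is below 15%, and the documents do not settle its direction. Section 4's warning of a possibly smaller effect in children concerns the halving; a smaller effect would lower power at every control rate in the table.

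**What to change.** In section 6, replace the 94% with the power at 400 under the 15% assumption (about 72–77%). State the formula, give a source for the 15% and the halving or label them as assumptions, and show the sensitivity range. Then add wording such as:

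> When the baseline phase closes, and before any with-cannula outcome is analysed, the observed proportion of baseline patients reaching SpO2 95%, with its 95% confidence interval, will be used to recalculate and report the power and the smallest detectable reduction. The with-cannula group size will be set from that calculation within the maximum of 500 patients in total. If 80% power cannot be reached within that maximum, the achieved power will be stated and a non-significant result will not be interpreted as absence of benefit.

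The stated purpose of the 500 maximum must be widened, since at present it covers only balancing the groups.

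The cost is a paragraph of text and a short calculation on data already being collected, with no increase in the cap and type I error essentially unchanged. The downsides are a less favourable stated power, possibly longer with-cannula accrual within the cap, and reliance on an imprecise baseline estimate, which is why its interval should be reported with it.

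### The stated power is wrong: 371 patients for 80% does not follow from the stated rates, and 400 patients gives about 76–79%, not 94%

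*Combined protocol and SAP*

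**What the plan says.** All of the power reasoning is in section 6, Number of Subjects (Recruitment Target).

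- **Effect:** the calculation holds "if the baseline rate of reaching 95% SPO 2 is 15% of patients and this procedure reduces that rate by half".
- **First result:** 80% power at α = 0.05 "is reached for a one-tailed logrank test with a total of 371 patients".
- **Second result:** "Rounding up to 400 patients to accommodate incomplete datasheets would provide power of 94" per cent.
- **Allocation:** "200 in the baseline group without nasal cannula adjunct and 200 patients with implementation of nasal cannula adjunct".
- **Method:** "based on formulae in *Statistics in Medicine* 1982; 1:121-9". The formula and the hazard ratio are not written out.
- **Ceiling:** "we may enroll a maximum of 500 patients in the entire study", offered so that the cannula group can match a baseline group that runs above 200.

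Section 14 (Data Management) plans Kaplan-Meier curves and survival analysis for the primary outcome. It does not say whether the final test is one- or two-tailed.

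**The concern.** An 8% increase in sample size (371 to 400) is said to cut the chance of missing the effect from 20% to 6%. Power for a fixed effect grows with the square root of the number of events, so a gain of that size is not credible. The 371 also looks small for event rates of 15% and 7.5%. Finally, the added patients are described as cover for incomplete datasheets, yet they are credited with extra power.

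This is the only power justification for the primary outcome. A reader who accepts 94% would take a null result as fairly strong evidence against a halving. The figure also bears on enrolment, because it makes 400 look ample when the plan allows up to 500.

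**Working it through.** **Inputs (section 6).** Baseline rate 15%; cannula rate 7.5%; one-tailed α = 0.05 (z = 1.645); target power 80% (z = 0.842); 1:1 allocation. The mean event rate is (0.15 + 0.075)/2 = 0.1125. Under proportional hazards, 15% against 7.5% implies HR = ln(0.925)/ln(0.85) = 0.480.

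**Step 1: reproduce 371.** Freedman's formula for the number of events is (z_α + z_β)² × [(1 + HR)/(1 − HR)]².

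- With HR = 0.5: 2.4865² × 9 = 55.64 events.
- 55.64/0.15 = 370.95, which rounds to 371.

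The match is exact, but dividing by 0.15 assumes that 15% of all patients have the event, including those given the cannula.

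**Step 2: sample size with the halved rate in the cannula group.**

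- Freedman, HR 0.480: 50.0 events; 50.0/0.1125 ≈ 445 patients.
- Freedman, HR 0.5: 55.64/0.1125 ≈ 495 patients.
- Two proportions: 438 patients.
- Schoenfeld, HR 0.480: 45.8 events; 45.8/0.1125 ≈ 407 patients.

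None of the variants tried that uses the halved rate comes within 3% of 371.

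**Step 3: test 94% against the plan's own 371.** Accept 80% at 371 and scale:

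- Power at 400 = Φ(2.4865 × √(400/371) − 1.645) = 82.6%.
- N for 94% (z = 1.555) = 371 × [(1.645 + 1.555)/2.4865]² ≈ 614.

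This step does not depend on the choice of formula or on the event rates.

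**Step 4: power from the stated rates.** At 400 patients the expected number of events is 400 × 0.1125 = 45. Freedman power is Φ(√45 × 0.5203/1.4797 − 1.645) = 76.2%. The table gives one-tailed results at HR 0.480. The simulated logrank column shows two sets of runs (10,000 and 20,000 runs per sample size; the second used exponential times and common follow-up).

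| Analysable N | Freedman | Simulated logrank | Schoenfeld |
|---|---|---|---|
| 371 | 73.5% | 74.5–74.8% | 76.7% |
| 400 | 76.2% | 77.5–77.9% | 79.4% |
| 500 | 84.0% | 85.2–85.4% | 86.7% |

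A two-proportions calculation gives 76.8% at 400. If the hazard itself is halved (HR 0.5), 400 patients give 72.3% (Freedman) or 75.2% (Schoenfeld). Reaching 94% at HR 0.480 needs about 675 (Schoenfeld) to 736 (Freedman) patients.

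**Step 5: the allowance.** The extra patients number 400 − 371 = 29, or 7.25% of 400. If they only replace unusable records, about 371 are analysed and the first row applies.

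**Step 6: if the final test is two-tailed at 0.05.** Power at 400 is 65.5% (Freedman), 68% (simulation) or 69.3% (Schoenfeld). At 500 it is 75.1%, 77% or 78.7%.

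**The case against.** The 94% has no defence, but several points narrow the rest.

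- **371 is traceable.** It comes exactly from a recognised formula, and the cited article was not available for this check. This stands: the fault is the event fraction used, not the formula. The result still contradicts the stated halving.
- **A single replacement figure would be falsely precise.** This stands in part. At 400 the methods run from 76.2% to 79.4%, so a range or a named formula is needed. Every method still falls below 80%, though Schoenfeld's only just.
- **The 495 mixes inputs.** HR 0.5 from a 15% baseline implies a cannula rate of 1 − √0.85 = 7.8%, not 7.5%. The mean is then 11.4% and N about 488. This is correct, but it changes nothing of substance.
- **The two-tailed figures are supplementary.** Section 6 specifies a one-tailed test, and section 9 (Study Endpoints) uses one-tailed superiority in its ineffectiveness rule. This stands. The two-tailed results matter only because section 14 names no tail.
- **The 29 extra patients are a matter of wording.** The sentence could mean the power if all 400 prove usable. That is a possible reading, but 94% is wrong on it too.
- **The 500 ceiling is conditional.** It exists to balance a larger baseline group, and the figures at 500 assume equal groups. This stands and should be said in the plan.
- **The gap to the design target is small.** Against 80%, the one-tailed shortfall with 400 analysable patients is roughly 1–4 points. This is true, but the plan advertises 94%.

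**Conclusion.** The concern holds. The pair of 80% at 371 and 94% at 400 is internally inconsistent whatever the formula. Under the stated rates of 15% and 7.5%, with 1:1 allocation, a one-tailed α of 0.05 and all 400 patients analysable, power is about 76–79%. The 94% is therefore overstated by about 15–18 points, and the risk of missing a true halving is about 21–24% rather than 6%. If only 371 are analysable, power is about 73–77%.

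These results assume proportional hazards with HR 0.480; halving the hazard instead gives 72–75% at 400. They make no adjustment for the interim analysis in sections 8 and 9, which allows stopping for significance. Any alpha spent there would alter the final-test figures.

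The source of 94% cannot be established. Reading 400 as a per-group number would give 93.5% (800 in total, Freedman, HR 0.5), but nothing in the document confirms that.

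**What to change.** In section 6:

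1. Delete the 371 and the 94%.
2. Write out the formula, the hazard ratio and the mean event rate of 11.25%.
3. State that 400 analysable patients are expected to give about 45 events and, by Freedman's formula, about 76% power one-tailed (76–79% across methods).
4. State that 80% one-tailed power corresponds to about 445 analysable patients by the same formula (407–445 across methods), and that 500 in equal groups gives about 84%.
5. Name the tail of the final logrank test here and in section 14. If it is two-tailed, report about 65% at 400 and 75% at 500 instead.
6. Show the allowance for incomplete datasheets separately. If the 7.25% margin is kept, 445 analysable patients means 445/0.9275 ≈ 480 enrolled.
7. Say whether the 500 ceiling may be used for power as well as for balancing the groups, and whether the figures allow for the interim look.

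The cost is protocol wording and a less favourable stated power. No patients are needed beyond the existing ceiling. If the sponsor wants to keep the 80% target, planned enrolment rises above 400 but stays within it.
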